#### **9.10.4 Rescue medication**

Despite the absence of evidence, the American Academy of Otolaryngology- Head and neck surgery (AAO-HNS) recommends the use of rescue treatment to patients without hearing improvement. Hearing is considered improved if the change in hearing loss is 10 dB or more in the 3 contiguous frequencies compared to the worst hearing threshold of the affected ear as identified at study entry. Rescue medication consists of intratympanic administration of corticosteroids (Appendix 6). The type of drug and number of injections are not specified. Rescue medication may be proposed from-Day 14 only in patients without hearing

improvement as defined above. The rescue medication (date, dose, indication) should be recorded on the e-CRF.

## 10 STUDY ASSESSMENTS

Test equipment, test environment, and test procedures must meet all relevant national standards and guidelines. All audiologic testings should be conducted in a quiet testing environment meeting appropriate current standards. The patients should be seated in a comfortable position. Before each audiologic evaluation, a quiet period or lack of noise for 16 to 24 hours is required. **For a given patient, the same certified and trained audiologist will perform the tests.** Any exception should be justified.

### 10.1 Efficacy assessments

#### 10.1.1 Pure Tone Audiometry

Pure tone audiometry is considered the diagnostic gold standard for assessing SSNHL (11) (24). The primary purpose of pure tone audiometry is to determine the degree, type and configuration of hearing loss as its measurement covers the entire auditory pathway from the external ear to the cortex.

It is a standardized subjective hearing test in which air and bone-conduction hearing thresholds in decibels (dB) for a set of fixed frequencies between 0.25 kHz and 8 kHz are plotted on an audiogram for each ear independently.

Audiometry will be performed in order to determine the pure-tone air-conduction and bone-conduction thresholds for each ear according to the recommended procedure of the British Society of Audiology and the guidelines of the American Speech Language Hearing Association (ASHA).

The detailed procedures will be described in a specific manual. All materials will need to be calibrated before the study start and on a monthly basis, following ASHA, American Association of Audiology (AAA), American National Standards Institute (ANSI) recommendations and military standards where applicable (6), (7), (8), (9).

At the inclusion visit, pure-tone air-conduction testing should be immediately repeated at 1 and 2 kHz to determine that the subject provides reliable responses. Responses are considered reliable if retest thresholds at both frequencies do not exceed  $\pm 5$ dB of the previously obtained threshold response.

Pure tone air and bone conduction thresholds will be determined for each ear (best ear at first) at 0.25, 0.5, 1, 2, 3, 4, 6, and 8 kHz for air conduction and 0.5, 1, 2, 3, 4 kHz for bone conduction using the descending method of limits (modified Hughson Westlake procedure as follows: initial descent towards threshold is accomplished in 10-dB steps. Beginning with the first non-response, level is increased by 5-dB for each non-response and decreased by 10-dB after each correct detection response.

The baseline pure tone audiometry test is the last test performed at site within 24 hours prior to the first study drug administration. In case of longer time or if a pure tone audiometry test was performed elsewhere than at study site, the test should be repeated prior to the first study drug intake. If a screening test has been performed at the study site within 24 hours prior to the first study drug intake, there is no need to repeat it.

---

**The hearing threshold** is defined as the lowest audible level, measured twice out of three presentations for that patient. The thresholds at each frequency for each ear for both air and bone pure tone audiometry will be recorded on the e-CRF at each study visit. The information will be captured in case of no response because of profound hearing loss.

The **hearing loss** will be determined as follows: Difference between the mean hearing threshold at the 3 most affected contiguous test frequencies (air pure tone average) and the corresponding mean hearing threshold of the contralateral ear or values from a pre-existing audiogram (dated less than 2 years) for the same frequencies (mandatory for bilateral acute acoustic trauma).

The Pure tone average frequencies determined at baseline will remain fixed for all evaluations. In case of bilateral acute acoustic trauma leading to sudden sensorineural hearing loss, the most affected ear according to the inclusion criteria will be considered for the analysis. If both ears are equally affected, the right ear will be considered.

In case of one missing frequency in any of the post baseline measurement, the PTA will be determined on the 2 out of the 3 available frequencies. An absolute improvement of 10dB is considered clinically meaningful.

### 10.1.2 Speech audiometry

Speech audiometry is a diagnostic hearing test designed to test word or speech recognition. It has become a fundamental tool in hearing-loss assessment. In conjunction with pure-tone audiometry, it can aid in determining the degree and type of hearing loss. Speech audiometry also provides information regarding discomfort or tolerance to speech stimuli and information on word recognition abilities.

Speech audiometry will be performed according to the guidelines of the American Speech Language Hearing Association (10).

**The Speech recognition threshold** is the minimum hearing level at which the patient can correctly recognizes the speech stimuli 50 % of the presented speech material. Spondaic words are the usual and recommended test material for the speech recognition threshold; spondaic words are two-syllable words with equal stress on both syllables (e.g. birthday)

According to the ASHA guidelines, patients will be familiarized with the spondaic words prior to the test. Patients will listen to the list of words and indicate if any are unfamiliar. These words can be eliminated from the list. The median speech reception threshold (SRT) for normal listeners is 20 dB SPL (0 dB HL).

The standard amount of time given for the patient to respond is approximately four seconds. The list of spondees adapted to local languages will be standardized across all centers in a given country.

The speech recognition threshold will be recorded on the e-CRF.

**The speech discrimination or word recognition** is the ability to repeat correctly an open set of monosyllabic words at supra threshold intensity. **The word recognition score (WRS)** is the percentage of test words correctly repeated by the patient.

The test will be administered in a quiet room without any competing noise. Word lists are derived from a standard list with language-specific monosyllabic words.

Words are presented randomly to each ear separately, with contralateral masking. They are phonetically balanced, meaning that the speech sounds used occur with the same frequency as in the whole language. In order to alert the patient, patients will be instructed to repeat the word, as follows: *“(Say the word ...)”*.

At the inclusion visit (day 1) visit 2, words will be presented at 60dB and 80dB. The WRS (percent correct rate) will be further derived by computerization.

An absolute improvement of  $\geq 15\%$  is considered clinically meaningful.

### **10.1.3 Tinnitus**

Tinnitus is often associated with SSNHL. It is defined as the hearing of sound when no external sound is present. While often described as a ringing, it may also sound like a clicking, hiss or roaring.

If the patient presents tinnitus in both ears, only the severity of the tinnitus in the ear affected by SSNHL will be assessed on a numerical scale (NRS). For the Tinnitus NRS, the patients will be asked to rate tinnitus loudness “right now” on a scale scored from 0 (no tinnitus) to 10 (extremely loud). The Tinnitus NRS score will be recorded on the e-CRF at each study visit.

In addition, the patients will be given a diary for recording the presence and the severity of the tinnitus (if any) on a daily basis during the first 14 days of treatment.

### **10.1.4 Vertigo**

The presence and severity (if relevant) of the vertigo will be assessed on a numerical scale. For the vertigo NRS, the patients reporting vertigo will be asked to assess if present and rate its severity “right now” at V2, then in the past week from V3 on a scale scored from 0 (no vertigo) to 10 (extreme vertigo). The vertigo NRS score will be recorded on the e-CRF at each study visit.

### **10.1.5 QoL**

#### **1) EQ-5D-5L**

Hearing loss with tinnitus can affect the patient quality of life which can be assessed by various tools including EuroQoL (28).

EQ-5D is a standardized measure of health status developed by the EuroQoL Group in order to provide a simple, generic measure of health for clinical and economic appraisal. EuroQoL, consists of two parts: the health-status descriptive system (EuroQoL 5-dimension, EQ-5D) and the EQ visual analogue scale.

The EQ-5D-5L version records the level of self-reported problems according to five dimensions (mobility, self-care, usual activities, pain/discomfort, and anxiety/depression).

Each dimension is assessed based on a single question with five response levels (no problem, slight problems, moderate problems, severe problems and extreme problems), to indicate his/her health state by ticking the box next to the most appropriate statement in each of the five dimensions. This decision results in a 1-digit number that expresses the level selected for that dimension. The digits for the five dimensions can be combined into a 5-digit number that describes the patient’s health state.

The EQ VAS records the patient’s self-rated health on a vertical visual analogue scale ranging 0 to 100, where the endpoints are labelled “The best health you can imagine” (100) and “The worst health you can imagine” (0). The VAS can be used as a quantitative measure of health outcome that reflect the patient’s own judgement.

The EQ-5D-5L will be completed at every visit from visit 2. Results will be recorded on the e-CRF (see appendix 2).

## **2) The tinnitus functional index (TFI)**

The impact of tinnitus on quality of life will be also assessed through a specific scale, the Tinnitus functional Index (TFI) (26) (see Appendix17).

The TFI comprises 25 questions on the impact of the tinnitus on the individual behavior and feelings. It includes eight subscales that address the intrusiveness of tinnitus, the sense of control the patient has, cognitive interference, sleep disturbance, auditory issues, relaxation issues, quality of life, and emotional distress.

The TFI will be completed at every visit from visit 2. Results will be recorded on the e-CRF

### **10.1.6 Otoacoustic emissions (optional)**

Otoacoustic emissions (OAEs) are low-intensity sounds generated by the inner ear when the cochlea is stimulated by a sound (functioning outer hair cells of the cochlea). When sound stimulates the cochlea, the outer hair cells vibrate. The vibration produces a nearly inaudible sound that echoes back into the middle ear. The sound can be measured with a small probe inserted into the ear canal.

OAEs recording is an objective neurophysiological test reflecting the function of the inner ear outer hair cells (OHCs) (29).

People with normal hearing produce emissions. Those with hearing loss greater than 25–30 decibels (dB) do not produce these very soft sounds.

The evoked OAEs include the transient evoked otoacoustic emissions (TEOAEs) and the distortion products otoacoustic emissions (DPOAEs). TEOAEs and DPOAEs are either present (recordable) or absent (non-recordable) in physiological conditions.

Some authors suggested a potential role of TEOAEs and DPOAEs early evaluation in the prediction of the ISSNHL prognosis (48). The early detectability of TEOAEs and DPOAEs preceding pure tone audiometry hearing improvement might be explained by the high sensitivity of those testing modalities of changing the outer hair cells activity.

OAEs are measured by acoustic stimuli such as a series of very brief clicks to the ear through a probe that is inserted in the outer third of the ear canal. The probe contains loudspeakers that generate the clicks and a microphone for measuring the resulting OAEs. OAE testing requires no behavioral or interactive feedback by the individual being tested.

Two pure tones ( $f_1$ ,  $f_2$ ) are simultaneously presented at 2 separate frequencies. DPOAEs originate from the cochlea when the two tones are closely related frequencies that activate the cochlea at a specific region of the basilar membrane corresponding to the  $f_2$  frequency. The DPOAEs are thought to reflect the outer hair cells activity at the supra-threshold level (31).

For the TEOAE, a single brief click that covers a broad frequency range activates wide regions of the basilar membrane and reflects the OHCs activity at the threshold level (cochlear function).

Thus, although both evoked OAEs measure the OHCs function, they reflect different ranges of their activity. Presence or Absence of TEOAEs and DPOAEs will be recorded on the e-CRF at each study visit, at sites conducting these tests.

For each tested frequency, the results of the  $2f_1-f_2$  level and of the Signal-to-noise ratio S/N (in dB SPL) will be recorded in the e-CRF for DPOAE.

For each tested frequency, the results of the Echo SPL level and of the Signal-to-noise ratio S/N (in dB SPL) as well as the Whole Wave reproducibility (WWR) (%) of the test for each ear will be recorded in the e-CRF for TEOAE.

## 10.2 Safety assessments

Clinical safety will be routinely assessed by the medically-qualified study investigator.

### 10.2.1 Physical examination

A physical examination including height, weight, Body Mass Index (BMI) and evaluation of main body systems/regions, including: skin and mucous, eyes/nose/throat, pulmonary, cardiac, gastro-intestinal and neurological systems is to be conducted at the screening visit (Visit 1), End of treatment (Visit 5) and End of Study (Visit 6).

A specific attention will be paid to neurological, head and neck, as well as otologic systems. Care should be taken to examine and assess any abnormalities that have been indicated as potentially present by medical history.

### 10.2.2 Otologic and audiologic examination

Otoscopy is to be done just before each hearing assessment at every visit to rule out possible outer-ear abnormality, such as otitis media, tympanic perforation. It is part of the standard of care. Tympanometry will follow the otoscopy in order to test the condition of the middle ear and mobility of the eardrum (tympanic membrane) and the conduction bones by creating variations of air pressure in the ear canal. There is no need to repeat the tests if it has been conducted within 6 hours prior to the screening visit.

### 10.2.3 Vital signs

Vital signs including temperature, systolic (SBP) and diastolic (DBP) blood pressures, heart rate will be collected after 10 minutes rest in the supine position.

Vital signs will be measured at each study visit, if possible, prior to blood draw (when relevant).

### 10.2.4 Electrocardiogram (ECG)

A standard digitalized 12-lead electrocardiogram (ECG) will be performed at baseline (Visit 2) prior to randomisation, on Day 7 (Visit 3), Day 14 (Visit 4), and End of treatment visit Day 28 (Visit 5). Each ECG will be triplicated. Ideally at V4 and V5 least one of the PK samples MUST be collected within 15 minutes of the 3rd ECG test being performed.

Heart rate will be recorded from the ventricular rate and the PR, QRS and QTc ( $QTc = QT / [60 / \text{heart rate}]^{1/2}$ ) intervals will be recorded. The digitalized ECG, collected in triplicate, will be managed with a central reading. Corrections of the QT interval will be calculated using Fridericia's and Bazett's formula. Changes from the baseline QT interval will also be assessed.

### 10.2.5 Laboratory safety

A standard laboratory blood test will be performed at the screening visit (Visit1), on Day 14 (Visit 4), and End of treatment visit Day 28 (Visit 5) also performed in case of Early termination between Visit 2 and Visit 5. Routine serum hematology and chemistry samples will be collected in EDTA tubes and according to the study flow chart. They will be kept at the local

---

laboratory as per laboratory requirements and outlined in the investigator manual which will be available at each investigational site.

The standard laboratory blood test comprises:

- haematology: complete blood count (CBC) including haematocrit, haemoglobin, red blood cell count, white blood cell count with differential count and platelets,
- Serum chemistry including: sodium, potassium, chloride, calcium, phosphorous, urea, creatinine, creatinine clearance (calculated with the Cockcroft-Gault formula for patients <65 years old and CKD-EPI creatinine equation or with MDRD equation for patients ≥65 years old), uric acid, total protein, albumin, lactate dehydrogenase (LDH), Alanine Aminotransferase (ALT), Aspartate Transaminase (ASAT), alkaline phosphatase, GGT and total bilirubin, fasting glycaemia (fasting is not required at baseline), creatine phosphokinase (CPK), triglycerides, cholesterol.
- Glucose (no fasting is needed at screening)
- C Reactive Protein (CRP).
- A urine or blood pregnancy test (in females of childbearing potential) will be performed at the screening visit, on D14 (Visit 4), end of treatment visit (D28 visit 5) and end of study visit (D 84 Visit 6). A subject cannot be included with a positive urine test. Blood sample will be taken for confirmation of the pregnancy status at baseline and end of study visit. In case of positive results, the pregnancy outcome should be reported. For practicability, urine samples may be replaced by blood samples.

No centralized laboratory procedure for laboratory safety is planned. Only local laboratories will be used.

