Day	Day-3 to Day 1	Inclusion Day 1	Day 7 (±2)	Day 14 (±2)	End of treatment Day 28 (±3)	End of study Day 84 (±3)
Study Visits	V1	V2	V3	V4	V5	V6
Pharmacokinetics/Biomarker						
Plasma samples for drug concentration				X	X	
Serum sample: Prestin		X 		X	X	

7 Serum sample for baseline prestin concentration measure will be taken before study drug intake (either at inclusion visit or screening visit)

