### 10.3 Pharmacokinetic evaluation

Serum samples will be collected for pharmacokinetic (PK) analysis on Day 14 (Visit 4) and End of treatment visit (Visit 5): for more details, please refer to the laboratory manual. Ideally at least one V4 and V5 PK samples MUST be collected within 15 minutes of the 3rd ECG test being performed. Blood samples will be drawn, handled and stored in a secure location as per laboratory requirements, outlined in the laboratory manual which will be available at each investigational site, until shipment. The date and hour of the last drug intake and blood sampling will be recorded.

Several samples will be batched together in the same shipment. The person in charge of the shipment will be contacted by the CRO who will organize samples' shipment. If the site needs to transfer the samples rapidly (due to storage constraint for instance), the CRO should be contacted.

PK samples will be destroyed after the finalization of the complete Clinical Study Report. No further uses of biological samples are planned, i.e. for additional research.

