### **11.1.4 Visit 4 (Day 14 ±2)**

The following tests and procedures will be performed:

- Checking for concomitant medication
- Inquiring about adverse event and fill an adverse event form if any
- The investigator or designee will check the IP and oral corticosteroids diary for compliance
- Checking the patient's diary for tinnitus
- Otologic examination and tympanometry

- Vital signs: blood pressure and heart rate, temperature
- 12-lead digitalised ECG
- Blood collection for routine hematology and serum chemistry (section 9.2.4)
- Serum sample for prestin and plasma sample for drug concentrations
- Audiometric tests: Pure tone audiometry and OAE tests (optional)
- Word and speech recognition Tests
- Pregnancy test (for WOCBP)

In case rescue medication is administered, please report in the e-CRF

The patient will be asked to complete specific questionnaires:

- Tinnitus and Vertigo Presence and Severity (NRS)
- QoL: EQ-5D-5L;
- TFI
- C-SSRS

The patient will be asked to complete a new patient diary for IP and corticosteroid compliance. The patient will be instructed to return his/her treatment carton and diary at the following visit,

The patient will be instructed to return all used and unused study treatment bottles at the following visit and to come in a fasting condition.

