### 6.13 Pharmacokinetic Analyses

Serum samples will be collected for pharmacokinetic (PK) analysis at pre- and post-dose on Day 14 (V4) and on Day 28 (EoT). Plasma concentration values will be summarized at each relevant timepoint by treatment group using number of non-missing observations, geometric mean, geometric coefficient of variation (CV), defined as  $100 * \sqrt{(e^{s^2} - 1)}$  where  $s$  is the SD of the data on a log scale, minimum and maximum.

All PK data will also be listed.

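### Protocol 10.2.5 sends chemistry as well as haematology blood into EDTA tubes, contradicting its own serum chemistry panel; separately, the PK sample is called serum in some places and plasma in others.

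*Protocol*

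**What the plan says.** **Safety chemistry.** Protocol 10.2.5 gives one tube instruction for both panels: "Routine serum hematology and chemistry samples will be collected in EDTA tubes and according to the study flow chart". It then separates haematology from "Serum chemistry including: sodium, potassium, chloride, calcium, phosphorous, urea, creatinine", and the chemistry list goes on to "alkaline phosphatase, GGT and total bilirubin". The same section adds: "No centralized laboratory procedure for laboratory safety is planned. Only local laboratories will be used". It also points to local laboratory requirements and the investigator manual, but for how samples are kept, not for the tube.

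The flow chart and 10.2.5 schedule this blood test at Visit 1, Visit 4 (Day 14) and Visit 5 (Day 28). SAP 6.14.2 analyses the results as serum chemistry, with shift tables and a table of treatment-emergent marked abnormalities.

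**PK.** Protocol 10.3 reads "Serum samples will be collected for pharmacokinetic (PK) analysis on Day 14 (Visit 4"), and continues to Visit 5. The flow chart has "Plasma samples for drug concentration". Visits 4 and 5 (11.1.4 and 11.1.5) call for "Serum sample for prestin and plasma sample for drug concentrations". SAP 6.13 opens with serum collection and continues "Plasma concentration values will be summarized at each relevant timepoint by treatment group".

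**The concern.** EDTA is an anticoagulant, so blood drawn into it gives plasma or whole blood. It suits the blood count but not a serum panel. The instruction therefore contradicts the list that it governs. Three of the listed analytes are ones that EDTA is generally known to distort, and all three are in the SAP's marked-abnormality table. With local laboratories only, at about 50 centres, no central laboratory would standardise the tube or notice the error.

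What is at stake is how reliable three safety parameters are at any site that followed the sentence, and any patient-level decision that uses them. For PK, the documents do not tell the reader which matrix the single concentration table in each study part will describe.

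**Working it through.** No alpha, power or sample-size figure is involved, so the check sets the texts side by side.

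**1. Is another chemistry tube named?** No. Across the protocol and SAP, the EDTA sentence is the only tube instruction for chemistry.

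**2. How far could it reach?** The documents do not say how many sites would follow the sentence, so only bounds can be given. Part 1 has 111 randomised patients and three scheduled draws each: 111 × 3 = 333 chemistry samples. The affected number lies between 0 and 333 in Part 1, not counting screen failures, early-termination draws or repeats.

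**3. What would happen in the SAP table?** The direction of the EDTA effect is an assumption from general laboratory knowledge. No size is assumed, and the potassium entry assumes a potassium salt of EDTA. The limits are from SAP 6.14.2.

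| Analyte | Assumed direction | Low limits | High limits | Effect if EDTA is used at every visit |
|---|---|---|---|---|
| Potassium (mmol/L) | up | <3.2, <3.0 | >5.5, >6.0 | true low values masked; patients above a high limit at baseline leave that at-risk set |
| Calcium (mmol/L) | down | <2.0, <1.75 | >2.9, >3.1 | true high values masked; patients below a low limit at baseline leave that at-risk set |
| Alkaline phosphatase | down | none | >2.5 ULN, >5 ULN | true raised values masked; no false marked abnormality is possible |

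The last column follows from two SAP rules. Section 6.14.2 bases percentages on patients who do not meet the criterion at baseline (or have no baseline value) and who have a later value. Section 6.2.2 takes the safety baseline as the last value up to the date of first dose, which for laboratory tests is ordinarily Visit 1. A site using the same wrong tube at Visits 1, 4 and 5 would carry the artefact in the baseline too. False treatment-emergent events would arise mainly if the tube changed between visits, and otherwise where the baseline was missing or values lay near a limit.

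**4. What else uses these values?** Protocol 11.1.1 decides eligibility partly on the laboratory results. Protocol 12.6 has a general clause under which severe laboratory abnormalities are repeated and, if confirmed, treatment is stopped; a repeat in the same tube type would reproduce the artefact. The listed laboratory thresholds in 11.3.2 include none of the three analytes.

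**5. PK matrix, each mention.**

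| Serum | Plasma |
|---|---|
| Protocol synopsis | Flow chart |
| Protocol 10.3 | Protocol 11.1.4 |
| SAP 6.13, first sentence | Protocol 11.1.5 |
| SAP Table 14.4.1a | SAP 6.13, second sentence |
| SAP Table 14.4.1b | |

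That is five against four, with both words in consecutive sentences of SAP 6.13. Loose synonymy does not explain it, because the Visit 4 and Visit 5 lists contrast serum for prestin with plasma for the drug.

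**The case against.** The strongest reply is that the EDTA sentence is garbled on its face. Serum haematology is not a coherent term, and the chemistry matrix is stated correctly a few lines below. Local laboratories would normally use their own chemistry tubes whatever the protocol says. The interference is not described in the documents, and the EDTA salt is not named. Safety analysis is descriptive, and abnormal values are rechecked before permanent discontinuation. All of this stands, and it limits the point to a risk of unknown frequency. It does not remove the point, because the sentence is an operative instruction and the reference to manuals does not cover the tube.

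Three stronger readings are tempting, and the documents do not support them:

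- **A wave of false marked abnormalities in any arm.** The at-risk rule in SAP 6.14.2 means that consistent EDTA use would mostly remove patients from the count, and alkaline phosphatase has high limits only.
- **Exclusion 31 depends on the measured potassium.** It is worded as a history of conditions, with hypokalaemia as an example and no threshold. Screening potassium can inform eligibility only through the general laboratory review in 11.1.1.
- **PK samples come from two matrices and cannot be pooled.** Protocol 10.3 defers handling to one laboratory manual, and nothing shows that two matrices were collected.

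**Conclusion.** The EDTA instruction is wrong as written and should be corrected. It is most likely a drafting merger of two tubes, so distorted results are a possibility and not an established fact. Where the sentence was followed at all three draws, the main cost would be lost information on potassium, calcium and alkaline phosphatase, with screening review and the general clause in Protocol 12.6 resting on distorted values. This conclusion assumes the usual direction of EDTA interference and, for potassium, a potassium salt. The primary efficacy analysis, the sample size and the listed withdrawal thresholds are not affected.

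The PK conflict is real but is a wording inconsistency. The validated matrix cannot be determined from these documents.

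**What to change.** - In Protocol 10.2.5, state the tubes separately: haematology in EDTA tubes; chemistry in serum tubes or the local laboratory's validated chemistry tubes. Check that the investigator manual agrees.
- Ask each site which tube was used for chemistry. Before database lock, flag any chemistry results obtained from EDTA blood, so that the SAP 6.14.2 tables can be read accordingly.
- Use one PK matrix term, the one in the laboratory manual and the validated assay, in the protocol synopsis, flow chart, 10.3, 11.1.4 and 11.1.5, and in SAP 6.13 and Tables 14.4.1a and 14.4.1b.

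The cost is a wording change, a check of the manuals and a short site query. No analysis or sample-size change is needed.
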